#### Definition of baseline for safety analyses

The last available assessment prior to the start of study treatment is defined as ‘baseline’ for safety analyses. If an assessment is planned to be performed prior to the first dose of study treatment in the protocol and the assessment is performed on the same day as the first dose of study treatment, it will be assumed that it was performed prior to study treatment administration, if assessment time point is not collected or is missing. If assessment time points are collected, the observed time point will be used to determine pre-dose on study day 1 (day of first dose of study treatment) for baseline calculation. Unscheduled assessments will be used in the determination of baseline. However, if time is missing, an unscheduled assessment on study day 1 will be considered to have been obtained after study treatment administration.

Participants who start and discontinue treatment on the same day may have two different sets of data collected on study day 1 (one during study and one in the End of Treatment (EOT) visit). Data reported at the EOT visit are not eligible for baseline selection.

If a scheduled pre-dose assessment actually occurred post-dose, then the corresponding assessment will be treated and analyzed similar to an unscheduled post-dose assessment.

Baseline for RR and QT/QTc interval assessments will be derived from the visit where both RR and QT are not missing. QTcB and QTcF will be derived based on RR and QT.

**Definition of baseline for immunogenicity analyses (Arms A and B in Cohort A and Cohorts B1 and B2)**

The last available assessment prior to or at the start of treatment with PF-06801591 (sample time  $\leq 0$  hr relative to PF-06801591 dose on Cycle 1 Day 1) is defined as ‘baseline’ for immunogenicity analyses. If an assessment is planned to be performed prior to the first dose of PF-06801591 in the protocol and the assessment is performed on the same day as the first dose of PF-06801591 but the assessment time point is not collected or is missing, it will be assumed that it was performed prior to PF-06801591 administration.

**Definition of baseline for biomarker analyses**

The last assessment prior to first dose of study treatment will serve as the baseline assessment for biomarker analyses. For biomarkers that are planned to be assessed on Cycle 1 Day 1, it will be assumed that the assessment was performed prior to study treatment administration, if the assessment time point is not collected or is missing.

**3.4.2. Baseline characteristics**

In Cohort A, randomization is stratified by the following, as recorded in the interactive response technology (IRT):

- Presence of carcinoma in situ at randomization (yes vs no);
- Geography (US vs Western Europe and Canada vs ROW).

The primary analyses for Cohort A of EFS and OS will be stratified by these randomization stratification factors.

Other baseline characteristics (including demographics, disease history, and prior anti-cancer therapies) are described in [Section 6.5.1](#). These baseline characteristics are not planned to be included as stratification variables or covariates in statistical models unless otherwise specified in [Section 6](#).

**3.5. Safety Endpoints**

**3.5.1. Adverse events**

**Treatment-Emergent Adverse Events**

Treatment-emergent adverse events (TEAEs) are those events with onset dates occurring during the on-treatment period.

**On-treatment period** is defined as the time from the first dose of study treatment through minimum (30 days + last dose of study treatment, start day of new anti-cancer drug therapy – 1 day) (also refer to Appendix 1 for irAEs). The start day of new anti-cancer drug therapy after the first dose of study treatment is derived as outlined in [Section 5.2.5](#).

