8.3.1. Time Period and Frequency for Collecting AE and SAE Information

The time period for actively eliciting and collecting AEs and SAEs (“active collection period”) for each participant begins from the time the participant provides informed consent, which is obtained before the participant’s participation in the study (ie, before undergoing any study-related procedure and/or receiving study intervention), through and including a minimum of 90 calendar days after the last administration of the study intervention.

For participants who are screen failures, the active collection period ends when screen failure status is determined.

Follow-up by the investigator continues throughout and after the active collection period and until the AE or SAE or its sequelae resolve or stabilize at a level acceptable to the investigator and Pfizer concurs with that assessment.

For participants who are screen failures, the active collection period ends when screen failure status is determined.

If the participant withdraws from the study and also withdraws consent for the collection of future information, the active collection period ends when consent is withdrawn.

If a participant definitively discontinues or temporarily discontinues study intervention because of an AE or SAE, the AE or SAE must be recorded on the eCRF and the SAE reported using the CT SAE Report Form.

Investigators are not obligated to actively seek AEs or SAEs after the participant has concluded study participation. However, if the investigator learns of any SAE, including a death, at any time after a participant has completed the study, and he/she considers the event to be reasonably related to the study intervention, the investigator must promptly report the SAE to Pfizer using the CT SAE Report Form.

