##### **Start and end dates of study treatment:**

For Arm A and Arm B in Cohort A:

The date/time of first dose of study treatment in a combination arm is the earliest date/time of the first non-zero dose date/time for any of the study drugs in the combination.

The date/time of last dose of study treatment in a combination arm is the latest date/time of the last non-zero dose date/time for any of the study drugs in the combination.

For Arm C (BCG only) in Cohort A and Cohorts B1 and B2 (PF-06801591 only):

The date/time of first dose of study treatment is the earliest date/time of non-zero dosing of the study drug.

The date/time of last dose of study treatment is the latest date/time of non-zero dosing of the study drug.

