### **5.2.7. Definition of on-treatment period**

Safety endpoints will be summarized based on the on-treatment period unless otherwise specified.

On-treatment period is defined as the time from the first dose of study treatment through minimum (30 days + last dose of study treatment, start day of new anti-cancer drug therapy – 1 day) (also refer to Appendix 1 for irAEs).

Safety data collected outside the on-treatment period as described above will be listed and flagged in listings but will not be summarized.

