#### **For BCG:**

Dosing in each period will be determined by the CRF disposition pages for when each period started and ended based on when participants started the next period.

- Induction: Dose Delay for Dose x (days) = Date of Dose x – Date of Dose (x-1) – 7,
- Re-induction: Dose Delay for Dose x (days) = Date of Dose x – Date of Dose (x-1) – 7,
- Maintenance:

Dose Delay for Dose x (days) = Date of Dose x – Date of Dose (x-1) – 7, for doses within a cycle (i.e. between Days 1, 8, and 15 of Cycle 4, Cycle 7, Cycle 13, Cycle 19 and Cycle 25).

Dose Delay for Dose x (days) = Date of Dose x – Date of Dose (x-1) – 70, between the last dose of the cycle prior to Cycle 7 and next dose (i.e. between Cycle 4 Day 15 to

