### Cycle 7 Day 1)

Dose Delay for Dose x (days) = Date of Dose x – Date of Dose (x-1) – 154, between the last dose of the previous cycle (Cycle 7 and after) and next dose (i.e. between maintenance cycles 7 to 25 from Day 15 to Day 1 (i.e. Cycle 7 Day 15 to Cycle 13 Day 1)

For Cohort A, dose delays will be grouped into the following categories, Cycles 1-3 and Cycle 4-25, for both BCG and PF-06801591.

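### The 30-day TEAE window depends on the dosing regimen, so Arm C events are modestly under-counted in participants who stop treatment inside a long BCG maintenance gap

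*SAP*

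**What the plan says.** SAP 3.5.1 counts an adverse event as treatment-emergent from first dose to the earlier of "30 days + last dose of study treatment" and the day before new anti-cancer drug therapy. SAP 5.2.7 and Protocol 9.4.2 use the same period. SAP 5.2.7 adds: "Safety data collected outside the on-treatment period as described above will be listed and flagged in listings but will not be summarized".

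What counts as the last dose differs by arm (SAP 3.4.1). For Arms A and B: "The date/time of last dose of study treatment in a combination arm is the latest date/time of the last non-zero dose date/time" of any drug in the combination. For Arm C: "The date/time of last dose of study treatment is the latest date/time of non-zero dosing of the study drug", which is BCG.

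SAP 6.5.3 gives PF-06801591 every 4 weeks to Cycle 25, and maintenance BCG on Days 1, 8 and 15 of Cycles 4, 7, 13, 19 and 25. The dose-delay formulas in SAP 6.5.3.4 state the planned BCG gaps in days: "70, between the last dose of the cycle prior to Cycle 7 and next dose", and "154, between the last dose of the previous cycle (Cycle 7 and after) and next dose" (for example "Cycle 7 Day 15 to Cycle 13 Day 1").

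Adverse event tables are numbers and percentages of participants (SAP 6.6.1). The SAE tables in SAP 6.6.3, and the on-treatment laboratory and ECG summaries, use the same window. Exposure is described (SAP 6.5.3.1), but no exposure-adjusted rate is planned. Collection itself runs "through and including a minimum of 90 calendar days after the last administration of the study intervention" (Protocol 8.3.1).

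**The concern.** In Arms A and B a dose every 28 days keeps the window open until close to the day treatment stops. In Arm C the window can close months before the stop, while the participant is still on the planned schedule and attending a Day 1 visit each cycle with adverse event collection. Two participants who stop on the same day, after the same follow-up, then contribute different amounts of time to the tables. A crude percentage does not adjust for that. At stake is a like-for-like reading of the added toxicity of PF-06801591, since the safety objective covers all three arms.

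**Working it through.** **Inputs.** The window rule, the definition of last dose and the schedules are those of SAP 3.4.1, 3.5.1, 6.5.3 and 6.5.3.4. Arm B is taken as BCG induction only, as in SAP 3.4.1. The dosage row of the table in Protocol 6.1 also lists maintenance BCG under Arm B, and the two must be reconciled. Discontinuation rates are assumed, because the documents give none.

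**1. Reproduce the gaps.** Study day of Cycle x Day y = 28(x - 1) + y.
- C7D15 = 183 and C13D1 = 337, so the gap is 154 days, as stated. C13 to C19 and C19 to C25 are the same.
- C4D15 = 99 and C7D1 = 169, so the gap is 70 days, as stated.

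**2. Window end by arm.** Window end = last dose before the stop + 30. For a stop on Day 1 of the cycle, before dosing:

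| Stop | Study day | A | B | C | A - C | B - C |
|---|---|---|---|---|---|---|
| C8D1 | 197 | 213 | 199 | 213 | 0 | -14 |
| C9D1 | 225 | 227 | 227 | 213 | 14 | 14 |
| C10D1 | 253 | 255 | 255 | 213 | 42 | 42 |
| C11D1 | 281 | 283 | 283 | 213 | 70 | 70 |
| C12D1 | 309 | 311 | 311 | 213 | 98 | 98 |
| C13D1 | 337 | 339 | 339 | 213 | 126 | 126 |

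At C13D1, Arm C's window closed 337 - 213 = 124 days before the stop. The pattern repeats in the two later gaps.

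**3. Average over one 154-day gap, stops evenly spread.** The first 14 days lose nothing against Arm A. Each following block of 28 days loses 14, 42, 70, 98 and 126 days.
- Against A: 28 × (14 + 42 + 70 + 98 + 126) / 154 = 9800 / 154 = 63.6 days.
- Against B: (9800 - 14 × 14) / 154 = 62.4 days.
- Share of stops losing at least 30 days against A: 112/154 = 73%. At least 60 days: 84/154 = 55%.
- In the 70-day gap against A: 28 × (14 + 42) / 70 = 22.4 days, maximum 42.

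**4. Completers.** Last doses fall on days 687 (A), 673 (B) and 687 (C), so windows end on days 717, 703 and 717. Arm C matches A and exceeds B by 14 days.

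**5. Effect on crude percentages.** Assume the same constant adverse event hazard in every arm, h = -ln(1 - p)/717, where p is the incidence over 717 days. Assume a constant stopping rate of -ln(1 - d)/687, where d is the proportion stopping before day 687. The expected percentage is the average of 1 - exp(-h × window end). Simulated results:

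| d | Mean window A / B / C (days) | p = 50%: A / B / C | p = 90%: A / B / C |
|---|---|---|---|
| 20% | 643 / 632 / 634 | 45.5 / 44.9 / 44.9 | 84.1 / 83.7 / 83.2 |
| 40% | 563 / 554 / 546 | 40.5 / 40.0 / 39.3 | 77.5 / 77.2 / 75.7 |
| 60% | 473 / 467 / 449 | 34.8 / 34.5 / 33.2 | 69.7 / 69.4 / 67.1 |

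For p from 5% to 90%, Arm C is 0.1 to 2.6 points below A, and from about equal to 2.3 points below B.

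**6. If stops cluster at disease assessments.** The 12-weekly assessments fall on Day 1 of C4, C7, C10, C13, C16, C19, C22 and C25. Stopping there before dosing costs Arm C 21, 42, 42, 126, 42, 126, 42 and 126 days (mean 567/8 = 71). Window ends are 87, 171, 255, 339, 423, 507, 591 and 675 in A, and 66, 129, 213, 213, 381, 381, 549 and 549 in C. The expected percentage is d × (mean of 1 - exp(-h × window end) over the eight visits) + (1 - d) × p, because A and C completers both reach day 717. At p = 50%, Arm C is 0.9, 1.9 and 2.8 points below A for d = 20%, 40% and 60%. The largest value, at d = 60% and p = 90%, is 74.8 against 70.4, or 4.4 points.

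**The case against.** Several defences stand. Protocol 9.4.2 prespecifies this window and descriptive summaries, and no between-arm safety test is planned. Immune-related events use a 90-day window (SAP Appendix 1), deaths are tabulated without the limit (SAP 6.6.2), and exposure is reported by arm. A participant who reaches the next BCG dose has no hole in the window. Under Protocol 7.1 one drug may be stopped alone, so an Arm A participant on BCG alone has Arm C's gaps. The error lowers Arm C, so it does not flatter PF-06801591. These limit the size of the problem, but they do not make the window equal across arms.

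A reader might infer four stronger things that the documents do not support.
- *That Arm C loses adverse event follow-up.* It does not. Events are collected, listed and flagged, and safety visits follow 30, 60 and 90 days after end of treatment. Only the summary tables leave them out.
- *That crude percentages are not comparable.* Under the assumed rates the distortion is a few points at most, and the number stopping in gaps is unknown.
- *That late BCG toxicity is hidden.* Protocol Appendix 14 describes monitoring after each instillation and symptoms lasting days. It does not describe onset beyond 30 days.
- *That a summary to 90 days after last dose would cure it.* That moves every arm equally. For a stop at C13D1 the ends are 309 + 90 = 399 in A and 183 + 90 = 273 in C, still 126 days apart.

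**Conclusion.** The point holds in a limited form. The summarized window depends on the regimen. For a stop inside a 154-day BCG gap it is 0 to 126 days shorter in Arm C than in Arm A (mean about 64), and between 14 days longer and 126 days shorter than in Arm B (mean about 62). The means assume evenly spread stops, and Arms A and B keep the longer window only while PF-06801591 continues. The under-count in Arm C is about 0.1 to 2.6 points against Arm A, if 20% to 60% stop at a constant rate that is the same in every arm and the event hazard is constant and equal. It would be somewhat larger if stops cluster at assessment visits, and could change if discontinuation differs by arm. The direction makes PF-06801591 look slightly worse. This is a cheap improvement to the safety tables and does not invalidate them.

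**What to change.** Keep the 30-day tables. For overall TEAEs, Grade 3 or higher TEAEs and SAEs, add by arm:

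1. Exposure-adjusted incidence rates: participants with an event per patient-year in the window.
2. A sensitivity summary whose window runs to 30 days after the later of last dose and the end-of-treatment or treatment-discontinuation date, still closing at new anti-cancer drug therapy. For a stop at C13D1 this ends on day 337 + 30 = 367 in every arm.

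The second addition matters more, because it brings the omitted events back and equalizes the window. The rates do neither: they correct only the denominator, and they assume a roughly constant hazard. If BCG events concentrate around instillations, leaving quiet gap time out of the denominator could raise Arm C's rate. Do not rely on a summary to 90 days after last dose as the remedy. The cost is a few extra tables from data already collected.

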## Adverse Events of Special Interest (AESIs)

AESIs are immune-related adverse events (irAE) and injection site reactions related to PF-06801591. The criteria for classification of an AE as an irAE are described in Appendix 1.

## 4. ANALYSIS SETS (POPULATIONS FOR ANALYSIS)

Data for all participants will be assessed to determine if participants meet the criteria for inclusion in each analysis set prior to releasing the database and classifications will be documented per Pfizer's standard operating procedures.

Only participants who signed informed consent will be included in the analysis sets below.

**Table 6. Analysis Sets**

Population	Description
Enrolled	All participants who sign the informed consent document (ICD)
Randomly Assigned to Study treatment (Full Analysis Set [FAS]) (Cohort A)	All participants who are randomized in Cohort A. Participants will be classified according to the study treatment assigned at randomization.
Full Analysis Set [FAS] (Cohort B1)	All participants who receive at least 1 dose of study drug and are BCG unresponsive with CIS according to BICR assessment.
Full Analysis Set [FAS] (Cohort B2)	All participants who receive at least 1 dose of study drug and are BCG unresponsive with papillary disease only.
Per Protocol (PP) (Cohort A)	Participants randomized in Cohort A excluding those who did not receive at least one dose of study drug, did not meet inclusion criteria 2 or 3, or met exclusion criteria 1 or 2.
Safety	All participants who receive at least 1 dose of study drug. For Cohort A, participants will be classified according to the study treatment assigned at randomization unless the incorrect treatment(s) was/were received throughout the dosing period in which case participants will be classified according to the first study treatment received.
Biomarker	The biomarker populations are a subset of the safety population and will include participants with at least 1 of the biomarkers evaluated at pre and/or post dose.
Immunogenicity	Subset of the safety population and will include participants who received at least one dose of PF-06801591 and have at least one ADA/Nab sample analyzed for anti-PF-06801591 antibodies.
PK	The PK concentration analysis population is a subset of the safety population and will include participants who have at least one post-1 st dose concentration measurement above the lower limit of quantitation (LLQ) for PF-06801591.  The PK parameter population is the same as the PK concentration analysis population.

[Table 7](#) summarizes the use of the analysis sets for efficacy, safety, baseline characteristics, PRO, and exposure.

**Table 7. Statistical Analyses by Analysis Set**

Endpoints	Full Analysis Set	Per Protocol Analysis Set	Safety Analysis Set
Baseline Characteristics	✓		
Prior and Concomitant Therapies	✓		
Exposure			✓
Efficacy: Primary	✓	✓ (EFS for Arm A vs Arm C, Cohort A)	
Efficacy: Secondary	✓	✓ (EFS for Arm B vs Arm C, OS, Cohort A)	
Safety			✓
PRO	✓		

## 5. GENERAL METHODOLOGY AND CONVENTIONS

### 5.1. Hypotheses and Decision Rules

#### 5.1.1. Hypotheses and sample size determination

##### Cohort A

Approximately 999 participants (including a minimum of 250 participants with CIS) will be randomized in a 1:1:1 ratio to one of the 3 treatment arms (A, B, or C) with approximately 333 participants randomized to each treatment arm in Cohort A, stratified by the presence of CIS (yes vs no) and geography (US vs Western Europe and Canada vs ROW).

The primary objective will be tested at a significance level of 0.025 (1-sided) associated with  $H_{01}$  described below:

$$H_{01}: HR_{EFS(AvsC)} \geq 1 \text{ vs. } H_{11}: HR_{EFS(AvsC)} < 1$$

where  $HR_{EFS(AvsC)}$  is the hazard ratio (HR) for EFS for Arm A vs Arm C.

In addition, the following statistical hypotheses will be tested to address the key secondary objectives:

$$H_{02}: HR_{EFS(BvsC)} \geq 1 \text{ vs. } H_{12}: HR_{EFS(BvsC)} < 1$$

$$H_{03}: HR_{OS(AvsC)} \geq 1 \text{ vs. } H_{13}: HR_{OS(AvsC)} < 1$$

$$H_{04}: HR_{OS(BvsC)} \geq 1 \text{ vs. } H_{14}: HR_{OS(BvsC)} < 1$$

[figure not shown]
where  $HR_{EFS(BvsC)}$  is the HR for EFS for Arm B vs Arm C,  $HR_{OS(AvsC)}$  is the HR for OS for Arm A vs Arm C, and  $HR_{OS(BvsC)}$  is the HR for OS for Arm B vs Arm C.

A graphical approach with group sequential testing outlined in Bretz et al. (2009) will be used to strongly control the family-wise type I error rate at a 1-sided 0.025 level as shown in Figure 3. The initial 1-sided alpha allocated to  $H_{01}$  is 0.025. If  $H_{01}$  is statistically significant,  $H_{02}$  and  $H_{03}$  will be formally tested at initial 1-sided alpha of 0.023 and 0.002, respectively. If

$H_{02}$  is statistically significant, alpha recycling will be applied to evaluate  $H_{03}$  at 1-sided 0.025 level. If  $H_{03}$  is statistically significant, all the alpha will be recycled to formally test  $H_{04}$ . One interim analysis on the OS endpoint is planned at the time of the EFS primary analysis. A Haybittle-Peto  $\alpha$ -spending function will be used to determine the efficacy boundary.

Based on Protocol Amendment 5, the IA2 will be removed, and the FA for EFS based on a calendar-based data cut-off date will be conducted. Randomization to Cohort A was completed on 16 November 2021 and the EFS FA data cut-off date will be set to allow for approximately 3 years of follow-up after last randomized participant. The treatment period was completed on 16 November 2023. Based on the observed pooled blinded data of EFS accrual rate, approximately 261 EFS events are expected to have occurred across all three arms. Assuming equal event rate across three arms, approximately 174 events for each two-arm comparison are expected by the EFS FA data cut-off date.

**Figure 3. Testing Strategy**

The power for EFS is estimated based on the following assumptions:

- median EFS for participants receiving BCG (induction and maintenance) is 24 months.
- treatment with PF-06801591 in combination with BCG (induction and maintenance) or BCG (induction only) is expected to increase the median EFS to 34.8 months, corresponding to a HR of 0.69 under the exponential model assumption.
- 20% drop-out rate for EFS within each arm.
- non-uniform participant accrual over 22 months.

- follow-up of approximately 33 months after the last participant is randomized.

For the primary endpoint, if the true HR is 0.69, 174 EFS events in Arm A and Arm C combined will provide 68.7% power to detect a difference using a 1-sided log-rank test at a significance level of 0.025.

Based on PA5, the FA for OS will be performed at the end of the study, which is approximately 5 years after the last participant has been randomized in Cohort A. Approximately 150 OS events are expected to have occurred across the three study arms assuming equal event rate across three arms (approximately 100 OS events for each two-arm comparison) by the OS FA data cut-off date.

If the primary objective is met, a gatekeeping approach will be used to allow further testing of the key secondary endpoints of EFS for Arm B vs. Arm C, OS for Arm A vs Arm C, and OS for Arm B vs Arm C as shown in [Figure 3](#).

- For the key secondary endpoint of EFS for Arm B vs Arm C ( $H_{02}$ ), if the true HR is 0.69 under the alternative hypothesis, 174 EFS events will provide 67.4% power to detect a difference using a 1-sided log-rank test at a significance level of 0.023.
- If both  $H_{01}$  and  $H_{02}$  are rejected, 100 OS events for Arm A vs C will provide 96.3% power to detect a HR of 0.472 using a 1-sided log-rank test at the 0.025 significance level and a 2-look group sequential design with Haybittle-Peto  $\alpha$ -spending function to determine the efficacy boundary. The hazard ratio of 0.472 corresponds to an increase in the 5-year Kaplan-Meier rate for OS from 0.80^13 in Arm C to 0.90 in Arm A, under the exponential model assumption.
- If  $H_{01}$  is rejected but  $H_{02}$  is not rejected, 100 OS events for Arm A vs C will provide 80.8% power to detect a HR of 0.472 using a 1-sided log-rank test at the 0.002 significance level and a 2-look group sequential design with Haybittle-Peto  $\alpha$ -spending function to determine the efficacy boundary.
- If  $H_{03}$  is rejected,  $H_{04}$  will be tested with the same power as  $H_{03}$  under the same assumptions.

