## 2. INTRODUCTION

This SAP provides the detailed methodology for summary and statistical analyses of the data collected in Study B8011006. This document may modify the plans outlined in the protocol; however, any major modifications of the primary endpoint definition or its analysis will also be reflected in a protocol amendment.

A separate SAP will cover the periodic safety review by the External Data Monitoring Committee (E-DMC).

Statistical analyses will be performed using cleaned electronic case report form (eCRF) data as well as non-CRF data (i.e., PRO, pharmacokinetic (PK) concentration, anti-drug antibody (ADA), neutralizing antibody (Nab), biomarker data, and Blinded Independent Central Review (BICR) of pathology, imaging, and oncology review data).

As of 31 August 2022, enrollment in Cohorts B1 and B2 was closed by the sponsor for business strategy reasons. This decision was not made due to any safety concerns, new emerging data, or regulatory interaction. Due to the decision to close enrollment in Cohorts B1 and B2, the Cohort B1 and B2 study objectives are no longer required.

As of 17 June 2024, the Protocol Amendment 5 revised the Cohort A study analysis plan for the primary and key secondary objectives. The rationale for this change is based on the observation from pooled treatment groups that EFS events are accumulating at a much slower rate than originally projected, together with an increasing rate of participants dropping out from EFS observation. The IA2 will be removed, and the FA for EFS based on a calendar-based data cut-off date will be conducted. Randomization to Cohort A was completed on 16 November 2021 and the EFS FA data cut-off date will be set to allow for approximately 3 years of follow-up after the last participant was randomized. The treatment period was completed on 16 November 2023. Based on the blinded observed EFS events accrual rate and assuming equal event rate across three arms, approximately 261 EFS events are expected to have occurred across all three arms (approximately 174 events for each two-arm comparison) by the EFS FA data cut-off date.

Data for Cohorts B1 and B2 will be reported at the time of PCD for Cohort A.

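### Does SAP section 5.1.1 attribute the 68.7% EFS power to planning inputs that do not produce it?

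*SAP*

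**What the plan says.** SAP section 5.1.1 sets out the EFS power in two steps.

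- **Event count.** The cut-off is set to allow "approximately 3 years of follow-up after last randomized participant". From pooled blinded data about 261 events are expected over the three arms, and then: "Assuming equal event rate across three arms, approximately 174 events for each two-arm comparison are expected by the EFS FA data cut-off date".
- **Power.** After the testing-strategy figure comes "The power for EFS is estimated based on the following assumptions", followed by five bullets: "median EFS for participants receiving BCG (induction and maintenance) is 24 months"; an experimental median of 34.8 months (hazard ratio 0.69 under an exponential model); "20% drop-out rate for EFS within each arm"; "non-uniform participant accrual over 22 months"; and "follow-up of approximately 33 months after the last participant is randomized". The next sentence gives 68.7% power from 174 events, a hazard ratio of 0.69 and a one-sided 0.025 log-rank test.

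The same section says that the key secondary hypotheses are tested only if the primary objective is met. It gives H02 (EFS, Arm B vs Arm C) 67.4% power at one-sided 0.023 with 174 events and a hazard ratio of 0.69.

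SAP section 2 explains why Amendment 5 changed the plan: "EFS events are accumulating at a much slower rate than originally projected", with drop-out from EFS observation also rising. Protocol section 9.2.1 states the 68.7% with the same three inputs and no list of planning assumptions.

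**The concern.** The lead-in says that the power comes from the list, but most of the list plays no part in it. Anyone who rebuilds the expected event count from the bullets finds far more than 174 events and power near or above 90%, and could conclude that either the list or the 68.7% is wrong. The 33 months in the list also differs from the 3 years given for the cut-off a few lines earlier.

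A second question attaches to H02. Its 67.4% stands under the gatekeeping sentence without being called stand-alone, conditional or joint. A reader could take it as the chance that the Arm B EFS claim succeeds through the gate, which is lower.

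If the power of the primary comparison were really misstated, the sponsor and regulators would have a wrong picture of the trial's chance of success after Amendment 5.

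**Working it through.** **1. Reproduce the plan's figures.** Inputs from SAP section 5.1.1: d = 174 events, HR = 0.69, 1:1 allocation within the comparison, one-sided alpha 0.025 (H01) and 0.023 (H02).

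Power = Φ(√d / 2 × |ln HR| − z)

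- √174 / 2 × |ln 0.69| = 6.595 × 0.3711 = 2.447
- H01: Φ(2.447 − 1.960) = 68.7%
- H02: Φ(2.447 − 1.995) = 67.4%

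Both match the SAP. The 174 is 261 × 2/3. The 0.69 is 24 / 34.8 = 0.6897. Drop-out, accrual, the 33 months and the absolute level of the medians do not appear in the formula.

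**2. What the whole list would imply.** Monthly hazards are ln 2 / 24 = 0.02888 in Arm C and 0.69 × 0.02888 = 0.01993 in Arm A. With drop-out hazard η and follow-up T, the expected proportion with an event is λ/(λ+η) × (1 − exp(−(λ+η)T)), averaged over entry times.

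Two inputs are missing from the SAP and are assumed here. The accrual distribution function is taken as (u/22)^g, with g from 0.5 (front-loaded) to 3 (back-loaded). Drop-out runs from 20% per year to 20% by 55 months (22 + 33).

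| Participants per arm | Fewest A+C events (g = 3, 20% per year) | Most A+C events (g = 0.5, 20% by 55 months) |
|---|---|---|
| 333 (planned) | 302, power 89.7% | 417, power 96.6% |
| 352 (1056 / 3) | 319, power 91.2% | 441, power 97.4% |

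A harsher case by hand: 333 per arm, everyone followed for only 33 months, 20% drop-out per year (η = −ln 0.8 / 12 = 0.0186).

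- Arm C: 333 × 0.02888/0.04748 × (1 − exp(−0.04748 × 33)) = 160.3
- Arm A: 333 × 0.01993/0.03852 × (1 − exp(−0.03852 × 33)) = 123.9
- Total 284, power 87.9%

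To bring the list down to 174 events, drop-out would have to be about 53% to 58% per year. The list and the 174 events therefore describe different event rates: 45% to 63% of A+C participants with an event under the list, against 174 / 704 = 25%.

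**3. The 33 months against 3 years.** With uniform accrual, 333 per arm and 20% drop-out per year, the list gives 316 events at 33 months and 323 at 36 months. The three-month difference does not explain the gap and does not touch the 68.7%.

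**4. H02 through the gate.** Assume a hazard ratio of 0.69 in both experimental arms and correlation 0.5 between the two test statistics (shared control arm). A bivariate normal calculation gives:

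- both H01 and H02 rejected: 53.3% (51.8% to 54.1% for correlation 0.4 to 0.55)
- H02 rejected given that H01 is rejected: 53.3 / 68.7 = 77.6% (75.4% to 78.8%)
- H02 alone: 67.4%, as stated

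**5. What depends on the unused inputs.** The EFS cut-off is set by calendar, about 3 years after 16 November 2021. Randomization is complete at 1056. The alpha split, the OS boundaries and the EFS analysis are all defined without drop-out, accrual or the 33 months.

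**The case for a change.** The best case for a change is that section 5.1.1 is where a reader checks the primary power, that the lead-in comes after the paragraph on blinded data and names a different basis, and that a few sentences would put it right. On H02, the neighbouring OS bullets are written conditionally, so the missing label is a real ambiguity, and 67.4% is about 14 percentage points above the 53% chance of passing the gate.

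The mismatch itself stands: the listed inputs do not give 174 events under any reading tried. Even drop-out of 20% every six months leaves about 237 to 247 events with 333 per arm. What does not stand is that anyone is misled about the power. The power sentence names its own three inputs, the paragraph before the list says where 174 comes from, and SAP section 2 says that the original projection failed. The first two bullets are also not idle, because they are the only stated derivation of the 0.69 in either document.

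That the remaining bullets are the original planning inputs is a fair inference, but neither document says so.

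On H02, the bullet states its hazard ratio, events and alpha, and the gate is explicit in the same section. Reporting power test by test is ordinary practice. The 53% needs two further assumptions, and the literal conditional reading, about 78%, makes 67.4% conservative.

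**Conclusion.** The concern does not call for a change. The lead-in in SAP section 5.1.1 is a clerical slip: it credits the power to a list of which only the hazard ratio is used, and the 33 months sits awkwardly beside the 3 years. The powers themselves, 68.7% and 67.4%, are exact for 174 events and a hazard ratio of 0.69, and their basis is disclosed in the same section, in SAP section 2 and, for the 68.7%, in protocol section 9.2.1. Rewording would alter no stated power, significance level, boundary, analysis, cut-off or participant number.

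The size of the mismatch, roughly 300 to 440 events against 174, rests on an assumed accrual shape and drop-out time scale; its direction holds under every reading tried. For H02, a stand-alone label or a joint probability of about 53% (hazard ratio 0.69 in both arms, correlation 0.5) would be extra reporting. It would not correct an error.
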